### III. SUBJECT SELECTION

**III.a. Field Trial inclusion/exclusion criteria:** Potential participants will be employed older health care workers (aged 50-65 years) who work a minimum of 4 night shifts (8-h) per month. The participants must have the willingness and ability to comply with the work and sleep intervention schedule, including: a) must report an ability to work three successive 8-h night shifts during two weeks; and b) must report an ability to spend 8 consecutive hours in bed attempting to sleep prior to the final two successive night shifts in the second study week. This means that individuals with a second job, child or elder care responsibilities, classes, or other non-optimal activities that would interfere with their ability to remain in bed attempting to sleep if randomized to an 8-h sleep group will be excluded. In addition, potential participants regularly taking prescription or over-the-counter medication(s) known to affect sleep [e.g., hypnotics] or alertness [e.g., antihistamines] will be excluded. In order that the participants are able to comply with the timing and duration of the 8-h afternoon-evening sleep intervention, they must have a typical commute time between their home and place of work of less than one hour.

**III.b. Field Trial Source of subjects and recruitment methods:** We will recruit up to 200 health care workers who regularly work 8-h night shifts to take part in the Field Trial in order to have up to 100 health care workers complete the entire Field Trial. We will recruit health care workers from hospitals as well as through the Massachusetts Nursing Association. We will use flyers, advertisements on websites and in newsletters, emails, internet posts, and postings on the MNA Facebook page. We will also use snowball sampling where participants may notify their coworkers.

We have selected health care workers as the occupational group in which to field test the sleep timing intervention because: (1) a large proportion of the health care workers population works night shifts; (2) night shift work has a negative impact on the safety and health of both health care workers and their patients; (3) more than half of US nurses are over age 50; (4) our prior experience has shown that health care workers are willing and valuable participants in research related to sleep and shift work; and (5) there is a large health care workers population in the surrounding community.

**III.a.b. Shift Worker Survey inclusion/exclusion criteria and recruitment methods:** We aim to enroll up to 1,000 participants in the Shift Worker Survey. We will use internet and newspaper advertisements and flyers to recruit employed individuals (20 or more hours per week) whose work includes overnight shifts [six or more consecutive hours between 10 pm and 7 am], with a minimum criterion of at least 4 night shifts a month. Both women and men aged 18 and older will be studied. We will recruit among all occupations, and include participants from throughout New England to take part in this web-based survey. Additionally, we will post notices in local hospitals and advertise on the Massachusetts Nursing Association Facebook page.

**III.a.b. Focus Group inclusion/exclusion criteria and recruitment methods:** We aim to enroll up to 60 individuals in virtual Focus Groups.

All health care workers in the Field Trial who are randomized to the 8-h afternoon/evening or the 8-h free sleep intervention groups will be invited to attend a virtual Focus Group discussion by secure videoconferencing

(via HIPAA-compliant & MGB-approved Zoom) so that we can gain in-depth information on the acceptability of the fixed 8-h sleep schedule from participants' perspective. We plan to enroll up to 30 individuals who take part in the Field Trial in Focus Groups. Virtual Focus groups will include health care workers who comply with the 8-h sleep intervention as well as those who do not comply or who withdraw from the intervention so that we may learn about facilitators and barriers for compliance with the fixed 8-h sleep schedule.

In addition to the health care workers who took part in the Field Trial, we will invite night shift workers who complete the Shift Worker Survey but indicate their inability to comply with a fixed 8-h sleep schedule to attend a remote Focus Group discussion. We expect that approximately half of the Shift Work Survey participants will indicate that they cannot comply with a fixed 8-h sleep schedule. We will email randomly chosen individuals from this cohort, inviting them to participate, until we achieve an enrollment of 30 individuals to gain in-depth information on challenges and barriers to adhering to an 8-h sleep schedule, as well as their opinions on what resources and facilitators at individual, interpersonal, and organizational levels could be used to promote use of such sleep strategies.

#### **IV. SUBJECT ENROLLMENT**

**IV.a. Methods of enrollment, procedures randomization.** After completing the Shift Worker Survey, participants will be asked if they are a health care worker. If they are, they will be informed that they can complete an additional Health Care Worker Questionnaire and following that they may be eligible for the Field Study. They will have the option of completing the Health Care Worker Questionnaire at the same time or logging on later to complete it. Individuals who complete both surveys and who meet the inclusion/exclusion criteria will be informed within the survey that they are eligible for the Field Study. If they indicate that they want more information, they will be provided with a description of the Field Study and the Consent Form, as well as contact information for our study recruiter. We will also ask them to provide us their contact information if they wish to be contacted about the study. The potential Field Study participant will be scheduled for a consent visit during which a member of the study team will review the study, equipment, and requirements. At the end of that visit the dates for the study will be decided, based on the participant's schedule of night shifts. As described below, randomization into one of three groups will be done during the study Intervention Week.

**IV.b. Procedures for obtaining informed consent** Participants in the Field Trial will provide written informed consent in person or remotely by secured video conference or phone. When remotely, subjects will sign the informed consent form using RedCAP informed consent module prior to enrolling in the study. One of the co-investigators or the Post-Doctoral Research Fellow will explain details of the study procedures including the randomization process, study duration, baseline and intervention block data collection process, and then obtain consent from each participant before the study begins.

Informed consent for the Shift Worker Survey was waived by the Partners Human Research Committee in their initial review. Participants will be given a statement about the research based on the Partners Human Research Committee "Informed Consent in Online Research" guidelines in the beginning of the REDCap survey.

Procedures related to the virtual Focus Group will be included in the Consent Form for the Field Study for participants who completed the Field Trial. Night shift workers who only completed the Shift Worker Survey and indicated their inability to comply with a fixed 8-h sleep schedule will receive a consent form only for the Focus Group.

#### **IV.c. treatment assignment and randomization.**

The field trial will use a randomized control trial design, where each participant will be randomized individually. Due to the anticipated small number of male participants, we will randomize by gender to ensure equal representation in each of the three intervention groups. The participants will be randomized to one of the 3 groups (at least 25 participants/group): A) control group (ad lib sleep); B) 8-h afternoon-evening sleep timing group; C) 8-h free sleep group.

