## VI. BIOSTATISTICAL ANALYSIS

### VI. a) Data variables, b) Study endpoints, c) Statistical methods

**Analysis of objective sleep duration and quality, and subjective sleep quality in the Field Trial.** Sleep data will be calculated in all participants from both blocks (Baseline vs. Intervention) using actigraphy. Duration of sleep (total sleep time, TST), number of awakenings, fragmentation index (FI) during the major sleep episode and subjective sleep quality from the e-diaries may be used as outcome measures to address Aim 1. After descriptive analyses, we may use linear and generalized linear mixed models to analyze main and interaction effects for factors condition (randomization group: ad lib sleep, 8-h afternoon-evening sleep, or 8-h free sleep) and shift (Baseline: B-Night 2, B-Night 3; Intervention: I-Night 2, I-Night 3). To account for inter-individual differences, we may incorporate into our statistical model a random intercept statement allowing for means to vary between participants. We will compare within subjects (shift) and between groups (condition).

**Field Trial analysis of performance and subjective alertness (Aim 2).** Each of the tests will be administered using an iPad app. Initial processing of tests will be calculated automatically (e.g., exact time of administration, scoring of alertness scales; mean and median reaction time; number of lapses, shortest (fastest 10%) and longest (slowest 10%) reaction times on PVT]. Following the descriptive measures, analyses of RT and lapses and subjective alertness data may be performed using linear and generalized linear mixed models to analyze main and interaction effects for factors condition (randomization group, as above) and shift (as above) with participant as a random effect.

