**Exploratory analysis of subjective stress and fatigue, recovery, mood, quality of life, and physiological stress in the Field Trial (Aim 2a).** Scores of acute subjective fatigue, inter-shift recovery, subjective stress, and quality of life will be calculated from the questionnaire administered at the end of Baseline and the end of Intervention. Mood will be assessed from visual analog scales administered three times per shift on nights 2 and 3 in the Baseline and Intervention blocks. Physiological stress will be assessed by analyzing cortisol levels in the optional saliva samples collected immediately after the third night shift in the Baseline and Intervention blocks. We will compare data from the Baseline to data from the Intervention for the three groups using linear and generalized linear mixed model analysis with factors condition (randomization group) and block (Baseline or Intervention) and incorporating a random intercept statement allowing for means to vary between participants.

**Field Trial exploratory analysis of scheduled 8-h afternoon-evening sleep vs. 8-h free sleep (Aim 2b).** We may compare results described above (sleep, performance and alertness, subjective stress, fatigue, recovery, mood, quality of life, and physiological stress) between the two scheduled sleep groups to determine whether the timing of an 8-h sleep episode has a significant impact on any of the outcomes. For this analysis, data from the 8-h free sleep group will first be examined for the time of day at which it occurred. Those participants who self-selected an afternoon-evening sleep episode will be classified with the 8-h afternoon-evening sleep group. We will carry out the analyses described above using linear mixed model analysis with factors condition (randomization group) and block (Baseline or Intervention) or night, incorporating a random intercept statement allowing for means to vary between participants.

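### The Field Trial randomises by gender but names gender in none of its models, so standard errors for between-group contrasts are slightly too large if balance is achieved

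*Combined protocol and SAP*

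**What the plan says.** Section IV.c gives the reason for using gender in the allocation, "Due to the anticipated small number of male participants", and the method: "we will randomize by gender to ensure equal representation in each of the three intervention groups". It continues: "The participants will be randomized to one of the 3 groups (at least 25 participants/group"). It does not describe blocks or any other restriction within gender.

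Section VI lists the model terms by aim:

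- **Aim 1 (sleep):** "main and interaction effects for factors condition (randomization group: ad lib sleep, 8-h afternoon-evening sleep, or 8-h free sleep) and shift", with "a random intercept statement allowing for means to vary between participants". The paragraph plans both within-subject and between-group comparisons.
- **Aim 2 (performance and alertness):** main and interaction effects "for factors condition (randomization group, as above) and shift (as above) with participant as a random effect".
- **Aim 2a (stress, fatigue, mood, quality of life, cortisol):** "factors condition (randomization group) and block (Baseline or Intervention"), with a participant intercept.
- **Aim 2b (the two 8-h groups):** condition and block or night, with a participant intercept. Free-sleep participants who chose an afternoon-evening episode are first reclassified into the afternoon-evening group.

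None of these names gender, and nothing says that the Field Trial analysis will reflect the factor used in randomisation. Sex appears as an analysis factor only for the Shift Worker Survey (Section II, Aim 3).

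**The concern.** When allocation is balanced on a factor, that factor cannot contribute to the difference between groups. If the model leaves it out, its variance stays in the between-participant error. The reported standard error then describes a less precise design than the one that was run: confidence intervals are a little too wide, tests reject a little less often than the nominal level under the null, and a little power is lost.

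This concerns planned contrasts. Section VI announces between-group comparisons by condition, and the power analysis in Section VI.d is itself a two-group comparison.

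**Working it through.** **1. The plan's own sample size.** Section VI.d gives 25 per group, α = 0.05, 90% power (printed as β = 0.9), and TST with SD 84.4 min and a difference of 78 min. For two means, two-sided:

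n = 2(1.960 + 1.282)² × 84.4² / 78² = 24.6, so 25 per group.

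For the fragmentation index (SD 39.9, difference 37) the same formula gives 24.4, so 25. Both figures reproduce, and neither calculation adjusts for gender.

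**2. Size of the overstatement.** Let m be the share of men and g the gender difference in within-gender SDs of the analysed quantity. The documents give neither, so both are assumed. With exact balance across groups and a linear model:

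model SE without gender / true SE = √(1 + m(1 − m)g²)

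At m = 0.10 and g = 0.5 this is √(1 + 0.09 × 0.25) = √1.0225 = 1.011. At g = 1.0 it is √1.09 = 1.044. True two-sided type I error is 2[1 − Φ(1.96 × ratio)]. Power is for 78 min with the total SD held at 84.4.

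| m | g | SE ratio | Type I error without gender | Power without gender | Power with gender |
|---|---|---|---|---|---|
| 5% | 0.5 | 1.006 | 0.049 | 90.6% | 90.8% |
| 10% | 0.5 | 1.011 | 0.048 | 90.7% | 91.1% |
| 10% | 1.0 | 1.044 | 0.041 | 91.4% | 92.7% |
| 15% | 0.5 | 1.016 | 0.047 | 90.8% | 91.3% |
| 15% | 1.0 | 1.062 | 0.037 | 91.8% | 93.4% |
| 20% | 0.5 | 1.020 | 0.046 | 90.9% | 91.5% |
| 20% | 1.0 | 1.077 | 0.035 | 92.1% | 94.1% |

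**3. Which contrasts are affected.** A simulation used three groups of 25, 5 men in each (20%), two Baseline and two Intervention nights, a within-participant correlation of 0.5 (assumed) and 20,000 runs. Here g is in single-night SDs, with SD 84.4.

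| Contrast | g | Empirical SE | Model SE without gender | Model SE with gender |
|---|---|---|---|---|
| Intervention nights, between groups | 0.5 | 20.4 | 21.2 | 20.6 |
| Intervention nights, between groups | 1.0 | 20.8 | 22.8 | 20.6 |
| Condition by block (change) | 0.5 or 1.0 | 16.8 | 16.8 | 16.8 |

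The between-group ratios exceed those in step 2 because averaging two nights at correlation 0.5 cuts the within-gender variance to 0.75 of its single-night value. At g = 0.5 the ratio becomes √(1 + 0.16 × 0.25 / 0.75) = 1.026. A constant gender effect cancels in the change contrast. If gender also shifts the Baseline-to-Intervention change by 0.5 SD, the model SE of that contrast is 17.5 without gender and 16.8 with it.

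**The case against.** The strongest reply is that the contrast isolating the intervention is hardly touched. All groups follow their habitual sleep at Baseline, so the treatment effect lies in the condition-by-shift or condition-by-block interaction, where a constant gender effect drops out. This stands and limits the point to between-group contrasts, such as those on Intervention nights or the condition main effect. The documents give no evidence that gender modifies the change.

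Four further replies also stand, at least in part:

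- **Balance is a condition.** If allocation within gender were unrestricted, gender would contribute to the group difference by chance, and the unadjusted standard error would not be overstated on average. The stated purpose of equal representation suggests a restricted scheme, but the text does not confirm one. Without balance, the case for the term is ordinary covariate adjustment.
- **Aim 2b is different.** Its groups are no longer those randomised, so the balance argument does not carry over.
- **The formula is for linear models.** Section VI also allows generalised linear mixed models, for which these percentages were not derived.
- **The wording is permissive.** The models for Aims 1 and 2 are ones the team may use. The plan is silent on gender and does not exclude it.

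A reader might also infer that, with no blocks described, the plan is unlikely to reach 25 per group. The documents do not support that. Under unrestricted allocation, an exact 25/25/25 split of 75 people has a probability of about 1%, but with the planned maximum of 100 the chance of at least 25 in every group is about 91.5%. An undescribed block method does not show that none is used.

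**Conclusion.** The mismatch between design and analysis is real, and its consequence is minor. With exact balance, an assumed 10% men and an assumed gender difference of 0.5 to 1.0 SD, omitting gender makes the standard error of a between-group contrast in a linear model about 1% to 4% too large. At the lower end, power for 78 min is 90.7% instead of 91.1%. The figure rises with more men or a larger gender effect, reaching about 8% at 20% men and 1 SD.

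It would be easy to read the omission as biasing the treatment comparison or raising the false-positive rate. It does neither under balance: the estimated difference is the same with or without gender, and type I error falls below the nominal 0.05. Nor does the point extend to every Field Trial result, given the near-zero effect on the interaction and the regrouping in Aim 2b.

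**What to change.** In Section VI, pre-specify gender, as the randomisation factor, as a fixed effect in the Field Trial models for Aims 1, 2 and 2a. In the Aim 2b model include gender too, described as ordinary covariate adjustment and not justified by balanced allocation. Fixing this before the data are seen prevents its inclusion from becoming a later choice.

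The cost is one sentence in the plan and one degree of freedom per model. The sample size of 25 per group does not change. As a separate reporting detail, Section IV.c could state how balance within gender is achieved, for example whether permuted blocks are used.

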## V. STUDY PROCEDURES

**Protocol overview.** We will investigate the effectiveness, feasibility, and acceptability of an 8-h sleep intervention in older night workers in an operational environment. The overall goal of the **Field Trial** is to minimize sleep deficiency and negative outcomes resulting from that, including sleepiness and performance impairments during night shift work. The **Shift Worker Survey** is designed to understand some of the demographic and operational factors that enable or inhibit the ability of individual shift workers to adopt this intervention. The **Focus Groups** are designed to glean in-depth information from older shift workers who indicate that they are unable or unwilling to adopt an 8-h sleep timing intervention. Understanding these factors will assist in refining and targeting the intervention to those individuals who will be most likely to benefit from the intervention sleep timing strategy.

**Field Trial.** The experimental protocol of the field trial is divided into two blocks (see Protocol Schema), the Baseline block and the Intervention block, where participants will work at least 3 night shifts in a row within each block. For at least one week prior to the baseline block health care workers will work their usual shift schedule (i.e., no vacation/scheduled days off).

The Baseline Block consists of a week during which participants work at least three consecutive 8-h night shifts. The three night shifts are preceded by a day off. All participants will be instructed to continue their normal routines, maintaining their habitual self-selected sleep-wake schedule. Sleep-wake and light exposure patterns will be recorded continuously using actigraphy, and a daily sleep e-diary will be filled in within the first hour after awakening from each main sleep episode. Performance (attention), alertness and mood will be rated three times on each night shift (just prior to their shift, on a break during their shift, and immediately after their shift). The purpose of this Baseline segment is to obtain measures of sleep duration and consolidation (to address Aim 1), alertness, mood, and performance (to address Aims 2, 2a and 2b) when working night shifts following their typical sleep routine. Immediately after the third night shift, an optional saliva sample will be taken to measure stress level (cortisol) and each participant will complete a baseline questionnaire covering questions related to fatigue, recovery, stress, and quality of life (to address Aim 2a). Participants will be given a specially configured mini iPad on which the E-diary, the performance test, alertness and mood rates, and fatigue, recovery, stress and quality of life questionnaire are programmed on.

The Intervention Block is similar to the Baseline Block, consisting of at least three consecutive 8-h night shifts, with the participants wearing an activity monitor, maintaining a daily sleep e-diary, and rating alertness, mood and attention three times per night shift using a mini iPad provided by the investigators. At the end of the first night shift, the participant will be told about their randomization group. In the control group (Group A), participants will not be given any instructions about the timing or duration of their sleep, but will be instructed to follow their usual night shift sleep routine. In the 8-h afternoon-evening sleep intervention group (Group B), participants will be instructed to go to bed between 13:00 and 14:00 (depending on their individual commute time) and to remain in bed attempting to sleep for 8 hours (until 21:00-22:00) before the next two night shifts. In the 8-h free sleep group (Group C), participants will be instructed to remain in bed for 8 continuous hours before the next two night shifts, but will not be given any instruction regarding which 8 hours they should sleep. Immediately following the last night shift, the participant will have the option to take a saliva sample to measure their stress level (cortisol), and they will complete a follow-up questionnaire where their fatigue, recovery, stress, and quality of life will be reassessed to investigate any exploratory short-term changes resulting from the intervention schedule. After completion of the two blocks, the participant will send back the activity monitor and iPad in a prepaid secured return package by mail or an investigator will arrange to meet with the participant to retrieve the activity monitor, iPad, and cortisol sample. Within 3 months after completion of the study blocks the participant will be invited to take part in a virtual Focus Group by secure videoconferencing (via HIPAA-compliant & MGB-approved Zoom).

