### Field Trial outcome variables

Sleep measurements including Total Sleep Time, Fragmentation Index, Wake After Sleep Onset, and Subjective Sleep Quality will be measured during the Baseline block and during the Intervention block. Sleep episodes in all participants will take place at home during off-shift times and will be recorded using wrist actigraphy and daily sleep e-diaries (which will be completed in the first hour after waking from the main sleep episode).

Subjective Alertness During both the Baseline and Intervention blocks, participants will complete an alertness task on the iPad three times per night shift: Once just before the night shift, once during their shift break, and once immediately following the night shift. The alertness assessment will consist of the Karolinska Sleepiness Scale (KSS) and a non-numeric bipolar (sleepy-alert) Visual Analog Scale (VAS).

Sustained Attention During both the Baseline and the Intervention Blocks, participants will complete a psychomotor vigilance task on the iPad three times per night shift: Once just before the night shift, once during their shift break, and once immediately following the night shift. The psychomotor vigilance task (PVT) is a 5-minute validated test of visual reaction time (RT) in which the participant is asked to maintain the fastest possible RTs to a simple visual stimulus.

Subjective Mood During both the Baseline and the Intervention Blocks, participants will complete a mood questionnaire on the Ipad three times per night shift: Once just before the night shift, once during their shift break, and once immediately following the night shift. Non-numeric bipolar (happy-sad) Visual Analogue Scales (VAS) will be used to assess subjective well-being and mood.

Fatigue, Inter-Shift Recovery, Subjective Stress and Quality of life will be assessed by questionnaire on the iPad immediately after the third night shift in the Baseline block and after the third night shift in the Intervention block (151, 152, 124).

Physiological Stress will be assessed by collecting a saliva sample immediately after the third night shift in the Baseline block and after the third night shift in the Intervention block to measure cortisol in subjects who live in the greater Boston area. Cortisol will be assayed in the Brigham Research Assay Core.

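### Intervention-block saliva sample and questionnaire are set at the last shift in the procedures but at the third shift in the outcome definitions, and the two differ in any block longer than three shifts

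*Combined protocol and SAP*

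**What the plan says.** Section V allows blocks of more than three shifts. The Field Trial overview says "participants will work at least 3 night shifts in a row within each block", and the Intervention Block is described as "consisting of at least three consecutive 8-h night shifts".

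The Baseline Block paragraph fixes the stress assessments by shift number: "Immediately after the third night shift, an optional saliva sample will be taken", with the baseline questionnaire at the same point. The Intervention Block paragraph fixes them by position: "Immediately following the last night shift, the participant will have the option to take a saliva sample", followed by the follow-up questionnaire.

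The Field Trial outcome variables section uses the third shift of each block for both the questionnaire and the saliva sample; for the second block its words are "after the third night shift in the Intervention block".

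Section VI (Aim 2a) repeats the third shift for saliva in both blocks, but places the questionnaire at the end of each block without a shift number. Section VIII.a pays for saliva after the third shift in each week.

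On the assigned sleep, section V discloses the group at the end of the first Intervention shift. Participants in the afternoon-evening group are then told "to remain in bed attempting to sleep for 8 hours (until 21:00-22:00) before the next two night shifts", and the 8-h free sleep group's instruction covers the same two shifts. Section III.a describes the 8 hours in bed as falling "prior to the final two successive night shifts in the second study week".

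**The concern.** Aim 2a compares Baseline with Intervention values of cortisol, fatigue, recovery, subjective stress and quality of life across the three groups. Aim 2b may reuse these measures for the two scheduled-sleep groups. The comparison is cleanest when both measurements fall at the same point in a run of night shifts, and when the second follows a sleep that the trial assigned.

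The Intervention Block paragraph is the operational text that staff and iPad prompts would be expected to follow. If it is followed literally in a block of four or more shifts, both conditions can fail: the follow-up falls later in the run than the Baseline measurement, and the sleep just before it is not one of the two assigned sleeps. The Aim 2a model has factors for group and block and a random intercept. It has no term for shift number that could absorb the difference.

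**Working it through.** No sample size or power figure is involved, so the check is a comparison of the texts followed by a count over block lengths.

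**Step 1: the timing statements side by side.**

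| Place | Measure | Baseline | Intervention |
|---|---|---|---|
| V, Baseline Block | saliva and questionnaire | third shift | – |
| V, Intervention Block | saliva and questionnaire | – | last shift |
| V, outcome variables | saliva and questionnaire | third shift | third shift |
| VI, Aim 2a | saliva | third shift | third shift |
| VI, Aim 2a | questionnaire | end of block | end of block |
| VIII.a, compensation | saliva | third shift | third shift |

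For saliva, the Intervention Block paragraph is the only outlier. For the questionnaire there are three descriptions: third then last (the two block paragraphs), third then third (outcome variables), and end then end (section VI).

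**Step 2: when the descriptions differ.** Let k be the number of shifts in the Intervention Block. Disclosure comes after shift 1, so the *next two* shifts are 2 and 3. The last shift is k, and its offset from the Baseline assessment at shift 3 is k − 3.

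| k | Last shift | Offset, k − 3 | Preceded by an assigned sleep (*next two* wording)? |
|---|---|---|---|
| 3 | 3 | 0 | yes |
| 4 | 4 | 1 | no |
| 5 | 5 | 2 | no |
| 6 | 6 | 3 | no |

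**Step 3: how common k > 3 is.** The documents do not say. Section II refers to three night shifts and section III.a to three successive shifts. Section VIII.a pays $15 × 3 shifts × 2 weeks = $90 for on-shift assessments and $50 × 2 = $100 for assigned sleeps. Four assessed shifts per week would give $15 × 4 × 2 = $120, which is not the stated total. Three therefore looks typical, but section V permits more.

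**Step 4: effect on the group contrast.** Let q be the share of participants with longer blocks, taken as equal across arms. Let δ be the mean shift-order offset, D the group difference at shift 3, and r the fraction of D still present at the later shift.

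- Each arm's mean change contains qδ. The term is the same in every arm and drops out of the difference between arms.
- The expected group difference is (1 − q)D + q·r·D = D[1 − q(1 − r)].

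If r = 1 there is no dilution; if r = 0 the contrast shrinks by q. The documents give neither q nor r, so no figure follows.

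**Step 5: which sleeps are assigned.** Under the *final two* wording the assigned sleeps precede shifts k − 1 and k. At k = 3 these are shifts 2 and 3, the same as *next two*. At k = 4 they would be shifts 3 and 4, against 2 and 3. Section VI analyses Intervention Nights 2 and 3, so in a longer block the two wordings would relate differently to the analysed nights.

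**The case against.** The strongest reply is that the assessed block is three shifts throughout. Sections II, III.a and VIII.a count three, the Baseline paragraph itself goes on to speak of the three night shifts, and section VI analyses only Nights 2 and 3 of each block. On that reading, last simply means third, and the outcome definition outweighs one loose word. This stands for three-shift blocks, where there is no effect. It does not settle longer blocks, which section V expressly allows without saying that only the first three shifts count.

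Four stronger readings are tempting, and the documents do not support them.

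- *That both measures are set at the third shift everywhere except the Intervention Block paragraph.* This is true for saliva. For the questionnaire, section VI says only the end of each block.
- *That shift order biases the comparison between groups.* The timing rule is the same in all three randomised arms, so a common offset largely cancels. It affects within-person change read on its own.
- *That the contrast shrinks by some stated percentage.* One could suppose that 10–40% of participants work longer blocks and that one unassigned sleep erases the whole effect. The documents support neither supposition, and the second is least plausible for quality of life.
- *That eligibility and procedures flatly contradict each other on the assigned sleeps.* The *final two* wording sits in a criterion about three successive shifts, where it agrees with *next two*. The two can diverge only if it is applied to longer blocks.

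**Conclusion.** The inconsistency is real and lies in operative text, but its reach is small. It has no effect in three-shift blocks. In a longer block, following the Intervention Block paragraph would put follow-up at least one shift later in the run than Baseline and, under the *next two* wording, after a sleep with no assigned schedule. Within-person change would then include shift order, and the group contrasts might be diluted by an amount that cannot be estimated from the documents.

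Only the exploratory Aim 2a outcomes and their possible reuse in Aim 2b are touched. Saliva is also optional and, under the outcome definitions, limited to participants in the greater Boston area. A reader might infer that the sleep and alertness results of Aims 1 and 2 are affected too. The timing of the saliva sample and questionnaire does not reach them, because those analyses name Nights 2 and 3. The separate wording on assigned sleeps would matter to them only if the *final two* description were applied to a longer block.

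The conclusion assumes that some Intervention Blocks exceed three shifts and that staff would follow the procedure paragraph as written. The protocol schema mentioned in section V was not available for this check and may settle the shift numbering.

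**What to change.** 1. In section V, Intervention Block, change *last night shift* to *third night shift* for the saliva sample and follow-up questionnaire.
2. In section VI, Aim 2a, replace the end-of-block timing of the questionnaire with the third night shift of each block, matching the outcome variables section.
3. Separately, reconcile the *final two* wording in III.a and the *next two* wording in V with each other and with the nights analysed in section VI, so that the text is unambiguous for blocks longer than three shifts. Which schedule applies is for the investigators to state.

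The first two changes are small wording corrections plus a check that the iPad prompts match. They add no visits, samples or participant burden, and leave the sample size unchanged. The third needs a decision by the study team and a matching clarification in the text.
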